The effect of caffeinate chewing gum on ice hockey performance after partial sleep deprivation: a double-blind crossover trial

Document Date: Aug 10, 2024

Project summary

The purpose of this study was to examine the impact of caffeinated chewing gum on the physical performance of elite ice hockey players in a partial sleep deprivation state. Fourteen national-level (Age: 25.2 ± 5.4 ; height: 176.5 ± 5.3 ; weight: 78.1 ± 13.4) ice hockey players were tested late at night after a full day of partial sleep deprivation. A randomised, double-blind experimental design was employed in which participants either chewed caffeinated gum (CAF) containing 3 mg/kg caffeine or a caffeine-free placebo gum (PLA) for 10 minutes prior to undertaking a series of tests on-ice and off-ice. The off-ice tests include a grip force, counter-movement jump (CMJ) and squat jump (SJ). The in-ice tests include 35 metre sprint, S-Shape agility test and Yo-Yo intermittent recovery test (Yo-Yo IR1 test).

Introduction

Ice hockey is one of the most popular sports in the world and has been an Olympic sport since 1920. Hockey is a high-intensity intermittent team sport. The players engage in periods of high-speed skating, interspersed with periods of passive recovery (1). It has been demonstrated that each skating session typically lasts between 30 and 80 seconds, with a subsequent recovery period of approximately 2 to 5 minutes. Similarly, for those engaged in ice hockey, it is essential to possess the requisite strength, agility, explosive power and aerobic endurance capacity (1). It can be argued that, in addition to their abilities on the ice, the physical capabilities of hockey players are also a significant factor in the sport.

The influence of circadian rhythm on exercise performance has been demonstrated in numerous studies (2). In general, the optimal time for exercise performance is usually in the evening due to the higher core body temperature, which leads to increased energy metabolism, improved muscle compliance, and promotion of actin-myosin cross-bridging (3). In accordance with the sleep model, the human circadian rhythm and the time since the previous period of rest both influence the characteristics of sleep (4). It can be reasonably deduced that modifying sleep schedules and circadian rhythm times may result in enhanced training quality. However, for athletes, student athletes, or when

competing abroad, sleep schedules and circadian rhythms may be out of control. Prior to major competitions, 64% of athletes report partial sleep deprivation (5). It can be reasonably deduced that partial sleep deprivation may have an impact on physiological rhythms, which in turn may affect athletic performance.

Caffeine is a beneficial nutrient that has been demonstrated to enhance athletic performance (6). It has been demonstrated that caffeine supplementation prior to exercise has a significant impact on improving endurance performance and reducing fatigue index in athletes. In sports requiring explosive power or agility, the effect size of caffeine was observed to be approximately small to moderate (7). In order to achieve a significant boost in pre-workout strength and explosiveness in explosive sports, a higher dosage of caffeine is required (8). However, supplementation with higher doses of caffeine may cause insomnia or affect sleep quality (9). One potential method for addressing insomnia may be to utilize smaller doses of caffeine prior to exercise, while still achieving a beneficial stimulant effect.

Caffeine gum can be absorbed through the mucous membranes of the mouth, resulting in a faster absorption rate of caffeine (10), which may also have a higher effect size on athletic performance (11). Based on past literature, chewing smaller doses of caffeinate chewing gum has been found to improve lower body strength and explosive performance (12). It may be posited that the use of chewing gum as a caffeine supplement could prove an effective method of enhancing athletic performance without adversely affecting sleep quality. Caffeine supplementation can be effective in improving explosive power and vertical jump height during fatigue after partial sleep deprivation (9). However, there are no published studies investigating the impact of partial sleep deprivation on the physical performance of ice hockey players, whether on-ice or off-ice. The purpose of this study was to examine the impact of ingesting caffeinate chewing gum on the on-ice and off-ice athletic performance of hockey players experiencing partial sleep deprivation.

Methods

Experimental Design

This study used a randomisation crossover design with a single-blind, double-blind experimental design. The participants were randomly assigned to either a caffeinated chewing gum trial (CAF) or a placebo trial (PL). After the first main trial, participants rested and recovered for 7-10 days before proceeding to the next trial. All participants completed all tests within one month. During the study period, all participants

maintained their normal training status, with no changes in the training program, and no over-training or extra competitions. This is the out-of-season training period for players.

Participants

Fourteen trained ice hockey players (Age: 25.2 ± 5.4 ; height: 176.5 ± 5.3 ; weight: 78.1 ± 13.4) were recruited to participate in this study, including six defensemen, two centres, and six forwards. All participants had more than 6 years of professional hockey training and were familiar with all hockey skills. Inclusion criteria: 1. 6 years of professional ice hockey training, 2. 6 months of continuous training, 3. 3 months of recovery from sports injuries such as strains and sprains. Exclusion criteria: 1. non-specialised ice hockey player. 2. has not trained regularly for the past 6 months. 3. has recovered from an athletic injury. 4. have been recovering from a sports injury for less than 3 months, or have epilepsy, hypertension, hyperlipidemia, heart disease, arthritis, osteoporosis, brain injury, or a history of caffeine allergy. In a past study, the effect of caffeinated chewing gum was found to have an effect size (Cohen's d) = 1.00 on the fatigue index of basketball players (11). The G*POWER statistical software (latest ver. 3.1.9.7; Heinrich-Heine-Universität Düsseldorf, Düsseldorf, Germany) indicated that eight participants were sufficient to interpret the data for the purposes of the study, with a power value of 0.8. In order to achieve a more precise POWER value, the number of participants in this study was set to 14. All participants provided written informed consent after being fully informed about the potential risks involved in the experiment, in accordance with the ethical standards of the relevant academic institution. A signed consent form was obtained from each participant. The order of participants was determined through the use of computerized randomization software (Excel Office 365). This study received approval from the Institutional Review Board of Jen-Ai Hospital - Dali Branch (202300071B0). All the data were performed at the indoor stadium. This study was conducted following the Declaration of Helsinki.

Protocol

All participants were required to perform the exercise-specific tests at least 2 times prior to the formal trial to familiarise themselves with the process of the formal trial. Participants were asked to record their diet 3 days before the first formal trial and were asked to repeat the same diet before the next trial. The following experiments were scheduled to start at 11 p.m. Upon arrival at the designated Ice hockey arena, the participants were granted a 10-minute rest.

All participants remained awake (CAF: 11.5 ± 2.2 hours; PL: 11.8 ± 2.2 hours) for a full day after adequate sleep (CAF: 7.4 ± 1.4 hours; PL: 7.1 ± 1.2 hours), with no nap allowed in between. After 10 minutes of breath, participants chewed either caffeinate chewing gum (CAF) containing 3 mg/kg of caffeine or caffeine-free chewing gum (PL) for 10 minutes each time. After spitting out the chewing gum, participants performed dynamic stretching and warm-up. After the warm-up, a 1-minute break was taken, followed by an off-ice test and an in-ice test. The measures employed in this study can be classified into two principal categories: off-ice tests and in-ice tests. In previous studies, a significant positive correlation has been identified between the off-ice tests and in-ice tests (13) Accordingly, the present study distinguished between off-ice and in-ice tests. The off-ice test includes grip force, counter-movement jump and squat jump (13). The in-ice test includes 35 metre sprint (13), S-Shape agility test (14) and Yo-Yo intermittent recovery test in ice (15). Participants were first tested on land, then after a 10-minute break and wearing ice equipment, they were tested on ice.

Outcome measure

The counter-movement jump was measured using Gymaware (GymAware, KineticPerformance, Australia). The device strap should be secured to the participant's waistband. The participant is instructed to remain as still as possible and place their hands on their waist. They are then required to squat down to the ground in a parallel position with their thighs, and then jump up as quickly as possible. The experimental procedure was conducted twice, with a one-minute interval between trials. The mean value of the two trials was calculated as the final result.

The squat jump was measured using Gymaware. The device strap should be secured to the participant's waistband. The participant is instructed to remain as still as possible and place their hands on their waist. They are then required to squat down to the ground in a parallel position with their thighs for 2-3 seconds, and then jump up. The experimental procedure was conducted twice, with a one-minute interval between trials. The mean value of the two trials was calculated as the final result. The same vertical jump test has been employed in previous study (11).

In the grip force test, the participant stood in a standing position holding a grip dynamometer (Smedley's Hand Grip Dynamometer TTM, Japan) (16) with the grip adjusted to the second knuckle and the arm at about 10-15 degrees to the trunk, and continuously pressed the grip for about 3 seconds at maximum force. Both hands were tested twice with a one-minute rest in between. The average strength of both hands was

taken as the result.

The 35 metre sprint on ice (13) was measured using a timing grating (Witty, Microgate, Bolzano, Italy) with an accuracy of 0.01 seconds. The first timing grate was placed at the starting position and the second timing grate was placed at the 35m position. Participants dressed in official ice hockey equipment, ready to remain stationary, holding the stick and retreated behind the starting line, began to complete the 35-metre sprint with maximum effort, during the process of the stick close to the ice surface, each experiment performed twice, with a three-minute break in the middle of the experiment, to adopt the best results.

The Ice S-Agility test is conducted using the timing grating (Witty, Microgate, Bolzano, Italy). The participant, wearing official hockey equipment and holding a stick, stands behind the half-ice goal and circles the two scrimmage circles in the half-ice, then sprints in a straight line across the blue line of the rink without touching the scrimmage circles and with the stick close to the ice surface. This approach has been used in the literature in the past (14). Each experiment was performed twice with a three-minute break and the best score was taken.

The on-ice Yo-Yo IR test measures the aerobic endurance of hockey players (15). Place the cone at the start point, the finish point (20m), and the buffer zone (5m after the start point). Participants stand on the ice wearing official hockey equipment and holding a stick. A 20-metre sprint is performed after hearing an instruction tone, with a 10-second rest period after every 2 sprints. During the test, the indicator tone will speed up with the longer time, during the process, if two consecutive times can not reach the opposite cone before the indicator tone, it will be judged as a failure, and the results of the previous stage will be recorded.

Caffeine and placebo gum

The caffeinated chewing gum used in this study, specifically Military Energy Gum (Arctic Mint flavor; Stay Alert, Chicago, USA), has been previously utilized in other studies (12, 17). Each piece contained 100 mg of caffeine, with a 5 g gum base. The gum was provided in various weights, according to the relative dosage. A commercially available blue mint gum was used as the placebo. To achieve a target dose of 3 mg caffeine per kilogram of body weight and maintain a double-blind design, all chewing gums were mashed, ground, homogenised, and reshaped after incorporating 0.3 g of peppermint flavouring powder. This ensured that the colour, appearance, taste, weight, and size of the gum types were indistinguishable. All chewing gums were prepared by

specialized individual and given to the on-site testers after numbering.

Statistical Analysis

All data are presented as means \pm standard deviations. The normality of the data distribution was assessed using the Shapiro–Wilk test. The grip force, CMJ, SJ, 35 metre sprint, S-Shape agility test and Yo-Yo intermittent recovery test were employed to analyses the through paired t-tests. The magnitude of the observed effects was quantified using Cohen's d, a measure of effect size. The power value of each data was conducted using G*Power 3.1.9.6 software (18). All data were calculated using SPSS (version 20, Chicago, IL, USA), and the significance level was $p < 0.05$.

Reference

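### Minor: replace the planned power value for each outcome with the mean difference and its 95% CI, and restate the planning power for the 14 players used

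*Protocol*

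**What the plan says.** **Statistical Analysis.** The section names six outcomes ("The grip force, CMJ, SJ, 35 metre sprint, S-Shape agility test and Yo-Yo intermittent recovery test were employed"), each compared by a paired t-test at the 0.05 level. Sidedness is not given. Results are to be shown as means and SDs. It continues: "The magnitude of the observed effects was quantified using Cohen's d, a measure of effect size". The next sentence reads "The power value of each data was conducted using G*Power 3.1.9.6 software (18"). No interval for the difference between conditions is mentioned.

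**Methods, Participants.** The sample size rests on one figure, a Cohen's d of "1.00 on the fatigue index of basketball players (11"). G*Power "indicated that eight participants were sufficient to interpret the data for the purposes of the study, with a power value of 0.8". Then: "In order to achieve a more precise POWER value, the number of participants in this study was set to 14". Neither a power nor a detectable effect is given for 14.

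**Introduction.** The only magnitude for performance of the kind tested here is qualitative: "In sports requiring explosive power or agility, the effect size of caffeine was observed to be approximately small to moderate (7"). Of gum, the text says it is absorbed faster, "which may also have a higher effect size on athletic performance (11").

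**Outcome measure.** The vertical jump test is said to have been used before in source 11, the same source that supplies d = 1.00.

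**The concern.** Six outcomes are tested in 14 players, so some non-significant results are quite possible. The reader will then want to know which effects the data still allow. The protocol attaches a power value to each result instead. If that value is computed from the observed effect, it restates the p-value on another scale: a large p always comes with a low power. It cannot separate the absence of a worthwhile effect from too little information.

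The planning paragraph does not fill the gap. Its power belongs to a different outcome and to a sample size that was not used. Adding players raises power and narrows estimates; it does not make a power value more precise. As written, a reader cannot see what 14 players could detect on any of the six outcomes.

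**Working it through.** **Inputs.** From the protocol: d = 1.00, n = 8 with power 0.8, n = 14 used, paired t-tests, significance level 0.05. Not in the protocol, so assumed and varied: one- or two-sided testing; whether d is the paired effect dz (mean difference divided by the SD of the differences) or a between-condition d (mean difference divided by the SD within a condition); the within-player correlation r; and any effect size for the six outcomes.

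**Formulas.** Power of the paired t-test comes from the noncentral t distribution with df = n − 1 and noncentrality dz × √n. With equal SDs in the two conditions, dz = d / √(2(1 − r)).

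**Step 1: the plan's own figure.** At dz = 1.00:

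| n | one-sided | two-sided |
|---|---|---|
| 7 | 0.754 | 0.600 |
| 8 | 0.815 | 0.681 |
| 10 | 0.898 | 0.803 |
| 14 | 0.971 | 0.932 |

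One-sided, eight is the smallest n that reaches 0.8, which matches the protocol. Two-sided, ten are needed. Eight can also be the two-sided answer if d is between-condition. For 80% power, n = 8 needs dz = 1.156 and n = 7 needs dz = 1.273. Solving r = 1 − 1/(2 dz²) with d = 1.00 gives r = 0.626 to 0.691. A two-sided normal approximation also gives eight: (1.960 + 0.842)² = 7.85, rounded up.

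**Step 2: what 14 players can detect.** Two-sided at 0.05, power is 80% at dz = 0.81. For an assumed between-condition d = 0.5:

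| r | dz | power |
|---|---|---|
| 0.3 | 0.42 | 0.31 |
| 0.5 | 0.50 | 0.41 |
| 0.7 | 0.65 | 0.61 |
| 0.8 | 0.79 | 0.78 |
| 0.9 | 1.12 | 0.97 |

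**Step 3: observed power at n = 14, two-sided, df = 13.** The observed dz is t/√14 = t/3.742.

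| p | t | observed dz | observed power |
|---|---|---|---|
| 0.05 | 2.160 | 0.577 | 0.52 |
| 0.20 | 1.350 | 0.361 | 0.24 |
| 0.50 | 0.694 | 0.185 | 0.10 |

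The column is the same for every outcome. If a between-condition d is entered where G*Power expects dz, the value entered is the observed dz × √(2(1 − r)). At p = 0.20 that is 0.361 × 1.183 = 0.427 at r = 0.3, giving 0.32, and 0.361 × 0.632 = 0.228 at r = 0.8, giving 0.12.

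**Step 4: what the interval shows.** The 95% CI half-width for the mean difference is 2.160/3.742 = 0.577 observed SDs of the differences. At p = 0.20 the interval is 0.361 ± 0.577, or −0.22 to 0.94 SD. At p = 0.50 it is 0.185 ± 0.577, or −0.39 to 0.76 SD. The first still allows a difference of 0.5 or 0.81 SD but not 1.00; the second still allows 0.5 but not 0.81. These are limits for the mean difference expressed in observed SDs, not confidence limits for the population dz. In practice they would be reported in kilograms, seconds and so on.

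**The case against.** The case for leaving the text alone has real force. Power rises with n, so under any reading that gives 0.8 at eight players, 14 players have more. Players and sleep hours are already reported in the past tense, so no design decision would change. Intervals are often left to an analysis plan, which may exist. Source 11 did use this trial's jump test, so the borrowed study is not remote from the outcomes here. The statement that effects are small to moderate concerns caffeine in general, and the text adds that gum may do better. All of this stands, and it makes the planning gap one of disclosure.

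It does not answer the main point. The protocol does not merely omit an interval; it names a statistic to stand beside each result, and that statistic is poorly chosen.

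Two caveats also stand. The sentence does not say that the power is observed; this is inferred from its place directly after the observed effects. And observed power is fixed by p and n only if dz is entered. If a between-condition d is entered as dz, the figure also moves with an unstated correlation. That distorts the number without making it informative.

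**Conclusion.** The point holds as a minor one. Read as observed power, the planned power value for each outcome cannot help to interpret a non-significant result, and a better quantity is available from the tests already planned. Secondarily, the only planning effect belongs to an outcome that is not measured, and the stated power belongs to eight players rather than 14.

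Two stronger readings are tempting, and the documents do not support them.

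- A reader might infer that the trial is underpowered. The protocol gives no numerical effect for any of the six outcomes and no within-player correlation. For an assumed between-condition d = 0.5, power at 14 runs from 0.31 (r = 0.3) to 0.97 (r = 0.9).
- A reader might infer that eight players at power 0.8 is an arithmetic error. It fails only for a two-sided exact test at dz = 1.00 (0.681); one-sided it gives 0.815, and other readings also lead to eight. The fault is that the sidedness and the type of d are not stated.

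The figures rest on two-sided testing at 0.05 unless marked otherwise, on complete data from 14 players, and on the assumed d and r values shown.

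**What to change.** **Statistical Analysis.** Replace the power value with the mean difference (caffeine gum minus placebo gum) and its 95% CI for each of the six outcomes, taken from the planned paired t-tests. Keep Cohen's d and say which type it is. Interpret non-significant results from the interval.

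**Methods, Participants.** State the power for the sample used, for example: With 14 players, a two-sided paired t-test at 0.05 has 80% power for a standardised paired difference (dz) of 0.81. Say that d = 1.00 was borrowed from a fatigue index not measured in this trial, and give its type and the sidedness behind eight (with the correlation, if it is a between-condition d). Quote 93% power at 14 only if that d is confirmed to be dz = 1.00; as a between-condition d it would give 0.83 at r = 0.3 and 0.99 at r = 0.7.

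**Cost.** Two text edits and six intervals; no extra players and no change to the tests. The power for d = 1.00 does not become less favourable, but the text would then show that it does not extend to smaller effects.

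### Eight players do not give power 0.8 at d = 1.00 for a two-sided paired t-test on the usual reading of d: power is 0.68 and ten are needed, though the 14 set are enough

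*Protocol*

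**What the plan says.** The sample size statement is in the protocol under Methods, Participants. It takes a Cohen's d of 1.00 for caffeinated gum on the fatigue index from a study of basketball players, names G*Power 3.1.9.7, and reports that the software "indicated that eight participants were sufficient to interpret the data for the purposes of the study, with a power value of 0.8". It then says that, to obtain a more precise power value, "the number of participants in this study was set to 14".

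That passage does not name the test, the alpha or the number of tails. Nor does it say whether d is standardised by the SD of the within-player differences or by the SD between players.

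The rest has to be taken from other sections. Experimental Design says "This study used a randomisation crossover design", so each player serves as his own control. Statistical Analysis lists the six performance measures, which "were employed to analyses the through paired t-tests", and sets the significance level at p < 0.05 without saying one- or two-sided. The purpose at the end of the Introduction is to examine the impact of the gum, with no direction given.

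**The concern.** An effect size, a power, a sample size, a test and a level are all stated, so the calculation can be checked. With the conventional choices (two-sided 5% level, d taken as d_z), the stated pair of eight players and power 0.8 does not come out. It comes out directly if the test is one-sided, but the protocol declares no one-sided test.

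What is at stake is the accuracy of the published justification. If the tests are two-sided and d is d_z, the power attached to eight players is overstated by about 12 percentage points. If a one-sided calculation was intended, the Statistical Analysis section needs to say so, because a one-sided 5% test allows a false claim of benefit 5% of the time per test, against 2.5% for a two-sided 5% test. A reader cannot tell from the protocol which case applies.

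**Working it through.** **Inputs**
- d = 1.00, power 0.8, n = 8 and the enrolled number 14: Participants.
- Two-condition crossover: Experimental Design.
- Paired t-test, alpha 0.05: Statistical Analysis.
- Number of tails: not stated; both are tried. Definition of d: not stated; d_z is taken first, then the alternative.

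**Formula.** For a paired t-test on n players, df = n − 1 and the noncentrality is d_z × √n. One-sided power is P(T > t_0.95,df), where T is noncentral t. Two-sided power is P(|T| > t_0.975,df).

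**Reproducing the plan's figure.** At n = 8 and d_z = 1.00 the noncentrality is √8 = 2.828 with df = 7. One-sided, the critical value is 1.895 and power is 0.815. At n = 7 one-sided power is 0.754. So eight is exactly the one-sided minimum for 0.80.

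**The same calculation two-sided.** At n = 8 the critical value rises to 2.365.

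| n | one-sided power | two-sided power |
|---|---|---|
| 7 | 0.754 | 0.601 |
| 8 | 0.815 | 0.681 |
| 9 | 0.862 | 0.748 |
| 10 | 0.898 | 0.803 |
| 14 | 0.971 | 0.932 |

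Two-sided, eight players miss d_z = 1.00 with probability 1 − 0.681 = 0.319, against the 0.20 implied by power 0.8. The minimum is ten. With eight players, the d_z detectable at 80% power is 1.156.

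**If d is not d_z.** If d = 1.00 is standardised by the between-player SD, equal in both conditions, and the between-visit correlation is r, then d_z = 1/√(2(1 − r)). At r = 0.5, d_z = 1.00 and the table applies. For eight players to reach 0.80 two-sided, d_z must be at least 1.156, so r must be at least 1 − 1/(2 × 1.156²) = 0.626, or about 0.63. Two-sided minimum n by r:

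| r | d_z | minimum n, two-sided | power at n = 14, two-sided |
|---|---|---|---|
| 0 | 0.707 | 18 | 0.687 |
| 0.3 | 0.845 | 14 | 0.832 |
| 0.5 | 1.000 | 10 | 0.932 |
| 0.6 | 1.118 | 9 | 0.971 |
| 0.7 | 1.291 | 7 | 0.994 |

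Eight is the smallest sufficient number for r of about 0.63 to 0.69, and it is more than sufficient above that.

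**Normal approximation.** Two-sided, n = ((1.960 + 0.842)/1.00)² = 7.85, which rounds up to 8. This also returns the plan's number, but it ignores that the SD is estimated on 7 degrees of freedom. The t-test that is planned still has power 0.681 at n = 8.

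**The case against.** The strongest reply is that the protocol contains no contradiction. It states neither the tails nor the definition of d, so both the two-sided reading and d = d_z are assumptions, and tails are often left to a statistical analysis plan, which is not shown here. The cited d may be standardised by the between-player SD, and a correlation of 0.63 or more between visits is plausible in the same trained players. The text says eight were sufficient, not that eight is the minimum, so any higher correlation would satisfy it too. Above all, nobody is running an eight-player trial: 14 were set.

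Much of this stands. A reader might infer that the figure can only have come from a one-sided calculation, or that the sample size statement and the decision rule describe different tests. The protocol supports neither inference. Two other routes lead to eight (a between-player d with high enough correlation, and a normal approximation), and the sidedness of the tests is not stated in either section. No one-sided decision rule is planned anywhere, so the 5% against 2.5% point is conditional.

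The reply does not rescue the figure as written. The protocol attributes it to G*Power and plans a t-test, so a normal approximation is not the calculation described. The correlation that the other route needs is not given. The usual reading of an unqualified p < 0.05, with a purpose that has no direction, is two-sided. On that reading, with d as d_z, the stated pair is wrong.

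**Conclusion.** The concern holds as a point about the stated calculation, at low severity. For the planned paired t-test, two-sided at 5% with d_z = 1.00, eight players give power 0.68 and not 0.8; ten are needed, 25% more than eight (10/8 = 1.25). As an exact paired t-test with d_z = 1.00, eight reaches 0.80 only one-sided.

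This rests on two assumptions that the protocol leaves open: that p < 0.05 is two-sided, and that d is d_z. If d is a between-player d and the between-visit correlation is about 0.63 or more, eight is adequate two-sided, but that has to be stated.

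It would be wrong to infer that the trial is too small for its own planning effect. On the same two assumptions, the 14 players set have power of about 0.93. Whether d = 1.00 for a fatigue index is a suitable planning value for the six measures analysed is a separate question, and nothing here bears on it.

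**What to change.** In the Participants section, state the test, alpha, number of tails and definition of d, and do one of the following:
- If d is d_z, replace eight participants with: *ten participants (paired t-test, two-sided alpha 0.05, d_z = 1.00, power 0.80)*, and add that the 14 players set give power of about 0.93.
- If d is standardised by the between-player SD, keep eight only if the assumed between-visit correlation supports it, and state that correlation and the resulting d_z.

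In the Statistical Analysis section, write *two-sided p < 0.05*.

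The cost is a couple of sentences. No extra players are needed, and the planned tests stay the same. On the first option the stated minimum becomes slightly less favourable.

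### The trial is presented as testing players in partial sleep deprivation, but the only account of their sleep calls it adequate, at about 7 hours

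*Protocol*

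**What the plan says.** The title names the state as the setting of the trial: "The effect of caffeinate chewing gum on ice hockey performance after partial sleep deprivation". The Project summary says that "ice hockey players were tested late at night after a full day of partial sleep deprivation". The Introduction claims novelty on the same ground, saying "there are no published studies investigating the impact of partial sleep deprivation on the physical performance of ice hockey players", and ends with a purpose that concerns "hockey players experiencing partial sleep deprivation".

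The Protocol subsection of Methods is the only place that describes how the players slept. It sets the time of testing ("The following experiments were scheduled to start at 11 p.m") and then says: "All participants remained awake (CAF: 11.5 ± 2.2 hours; PL: 11.8 ± 2.2 hours) for a full day after adequate sleep". The sleep figures and the only rule about sleep follow: "adequate sleep (CAF: 7.4 ± 1.4 hours; PL: 7.1 ± 1.2 hours), with no nap allowed in between".

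**The concern.** A reader of the title and purpose expects sleep that was curtailed, or wakefulness that was prolonged. The Methods describe neither. They report about 7 hours of sleep, describe it as adequate for all participants, and follow it with less than 12 hours awake on average, which they call a full day.

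The sleep state defines the condition under study, the claim of novelty and the athletes to whom a result would be applied. If the players were not deprived, a conclusion about caffeine gum after partial sleep deprivation has no support in this trial. The data cannot settle the matter afterwards. The two conditions, caffeine and placebo, share the same sleep state, so their difference in performance says nothing about whether that state was deprivation.

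**Working it through.** **Inputs** (protocol, Methods, Protocol subsection)

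| | Caffeine | Placebo |
|---|---|---|
| Sleep, mean ± SD (h) | 7.4 ± 1.4 | 7.1 ± 1.2 |
| Awake before testing, mean ± SD (h) | 11.5 ± 2.2 | 11.8 ± 2.2 |
| Start of testing | 11 p.m. | 11 p.m. |

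**1. Label against description.** The title, summary and purpose say deprived; the Methods say adequately slept. No outside definition of deprivation is needed to see the conflict, because the protocol supplies the word adequate itself.

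**2. Search for a passage that reconciles them.** The eligibility criteria (Participants) contain no sleep item. Experimental Design names only the caffeine and placebo trials. The only sleep rule is the ban on naps. No section restricts sleep or gives a cut-off in hours. Sleep and wake hours were recorded and reported, but there is no criterion to compare them with.

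**3. Clock times.** Assume that hours awake are counted to 11 p.m. and that sleep was one block ending at waking.

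- Caffeine: waking at 23:00 − 11.5 h = 11:30; sleep onset at 11:30 − 7.4 h = 04:06.
- Placebo: waking at 23:00 − 11.8 h = 11:12; sleep onset at 11:12 − 7.1 h = 04:06.
- Sleep plus wake: 7.4 + 11.5 = 18.9 h and 7.1 + 11.8 = 18.9 h.

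On these assumptions the mean figures describe sleep of about 7 h that began late. They could equally contain a misreported value. The protocol states neither.

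**4. Could individual players have slept short?** Mean − 2 SD is 7.4 − 2.8 = 4.6 h (caffeine) and 7.1 − 2.4 = 4.7 h (placebo). Since the protocol gives no cut-off, a range is shown, assuming normality, with P(sleep < c) = Φ((c − mean)/SD):

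| Cut-off c | Caffeine | Placebo |
|---|---|---|
| 5 h | Φ(−1.71) = 4.3% | Φ(−1.75) = 4.0% |
| 6 h | Φ(−1.00) = 15.9% | Φ(−0.92) = 18.0% |
| 7 h | Φ(−0.29) = 38.8% | Φ(−0.08) = 46.7% |

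At 6 h this is 14 × 0.159 = 2.2 and 14 × 0.180 = 2.5 players, so about 2 to 3 of 14.

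**5. Was wakefulness prolonged?** Mean + 2 SD is 11.5 + 4.4 = 15.9 h and 11.8 + 4.4 = 16.2 h. Under normality, 41.0% (caffeine) and 46.4% (placebo) were awake for more than 12 h. The 12 h mark is illustrative; the protocol sets none.

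**The case against.** The strongest defence is that the label means something else. The summary and the Methods both speak of a full day, so partial sleep deprivation might mean staying awake without a nap until late-night testing, rather than a shortened previous night. On that reading the hours are right and the fault is a poorly chosen, undefined term. This cannot be excluded, but the protocol never says it, and a mean of 11.5 to 11.8 h awake fits it badly. The Introduction also treats circadian rhythm and time since the last rest as two separate influences, so a late hour is not in itself sleep loss. Even if this reading is what was meant, the wording must change.

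Several narrower objections stand:

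- The spread leaves room for a few short sleepers. The tail percentages are only illustrative, since they assume normality from the mean and SD of 14 players and use cut-offs not in the protocol. The finding does not depend on them.
- Similar mean hours in the two conditions do not show that each player slept alike in both periods. What protects the caffeine–placebo comparison is the randomised order within players.
- For the stated purpose, the lack of a rested condition or of a sleep item in the eligibility criteria is not in itself a defect. It means only that nothing else in the document can establish the state.

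**Conclusion.** The concern holds and must be fixed. The protocol gives its players two incompatible descriptions, and the document alone does not show whether the label, the word adequate or the hours are in error. The conflict rests on the protocol's own words and four reported means. The assumptions about normality, clock times and a single sleep block serve only to size it.

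The consequence lies in what the trial may conclude. If the reported hours are correct, the headline claim about partial sleep deprivation is unsupported for the group as a whole, and so is the novelty claim. The paired comparison, the outcomes and the sample size, power and alpha figures are unaffected.

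**What to change.** First reconcile the title, Project summary, Introduction and Methods (Protocol subsection) against the recorded sleep and wake data. Then:

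- **If the reported hours are confirmed:** restate the condition in the title, summary and purpose as testing at 11 p.m. after adequate sleep, with the recorded hours awake. Replace the phrase a full day with those hours, and limit every conclusion to that state. This also covers the case in which the authors meant late-night testing or delayed sleep: say so, and drop the deprivation label.
- **If the records show that sleep was curtailed:** correct the description and hours in the Methods, and state in hours what counted as partial sleep deprivation and how it was checked.

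In either case, show sleep and wake hours by condition beside the results. The mean and SD are already in the protocol; the range would be new.

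The cost is a check of data already collected, followed by rewording. No new testing is needed on either route. The first route does have a scientific price: it narrows the stated question after data collection and weakens the claim of novelty, and the report should say so openly.
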